### **6.6.2. Vital Signs**

*Vital signs will be listed and tabulated by dose group and week with descriptive statistics. Change from baseline will also be summarized using the same descriptive statistics by dose group and month or week.*

### **6.6.3. Electrocardiogram**

*The following ECG data will be listed: QT, QTc (Fridericia's), heart rate, QRS duration, PR and RR interval.*

QTcF will be derived using Fridericia's heart rate correction formula:

$QTcF(\text{msec}) = QT(\text{msec}) / (RR * 1000)^{1/3}$  where  $RR(\text{sec}) = 60/\text{HR}$  (if RR is not provided)

*Baseline and change from baseline for QT, QTcF, heart rate, QRS, PR and RR will be summarized using descriptive statistics by treatment and study week. The baseline for ECG parameters will be the average of the triplicate pre-dose measurements at baseline. Any triplicate measurements will be averaged prior to the calculation of summary statistics. For QTcF a classification of absolute values and increase from baseline will be used.*

*The number of subjects with average of the triplicate QTcF <450 ms, 450 ms ≤ QTcF <480 ms, 480 ms ≤ QTcF <500 ms and QTcF values ≥500 ms will be tabulated by treatment and study week. The number of subjects with maximum increase from baseline QTcF <30 ms, 30 ms ≤ QTcF <60 ms and QTcF ≥60 ms will be tabulated by treatment and study week. In addition, the number of subjects with any single uncorrected QT values ≥500 ms will be summarized.*

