## **2.2. Endpoints**

### **2.2.1. Primary Safety-Based on Data from Period 1**

- Incidence of dose limiting or intolerability treatment related AEs by Week 49.
- Incidence, severity and causal relationship of treatment emergent AEs (TEAEs) and withdrawals due to TEAEs by Week 49.
- Incidence and magnitude of abnormal laboratory findings (clinical laboratory tests [hematology, chemistry, GGT, GLDH, PT, aPTT, creatine kinase, amylase, serum ferritin, serum iron, Total Iron Binding Capacity (TIBC), % transferrin saturation, hormone [luteinizing hormone [LH], follicle stimulating hormone [FSH], thyroxine [T4], thyroid stimulating hormone [TSH], fecal occult and urinalysis) by Week 49.
- Abnormal and clinically relevant changes in liver MRI by Week 45 and physical examinations (including nose and throat mucosal exam and Tanner stage), weight, vital signs, ECG, cardiac MRI or echocardiogram measured LVEF (and other exploratory cardiac endpoints), DXA-spine (bone mineral density), x-ray (hand and wrist for bone age evaluation) and C-SSRS (See [Appendix 1](#) and [Appendix 2](#)) parameters by Week 49. Cardiac MRI with gadolinium is the preferred method for cardiac imaging. If the subject has a contraindication to gadolinium, cardiac MRI without gadolinium will be acceptable. Echocardiogram may be substituted if it is not possible to perform cardiac MRI.

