### **7.2.5. Electrocardiogram (ECG)**

ECGs should be collected at times specified in the [Schedule of Activities](#) section of this protocol.

All scheduled ECGs should be performed after the subject has rested quietly for at least 10 minutes in a supine position.

Triplicate 12-lead ECGs will be obtained *approximately* 2-4 minutes apart; the average of the triplicate ECG measurements collected at Baseline (Visit 2), will serve as each subject's time-controlled baseline QTc value.

To ensure safety of the subjects, a qualified individual at the investigator site will make comparisons to baseline measurements. If the QTc interval is increased by  $\geq 45$  msec from the baseline, or an absolute QTc value is  $\geq 500$  msec for any scheduled ECG, then 2 additional ECGs will be collected, approximately 2-4 minutes apart, to confirm the original measurement. If either of the QTc values from these repeated ECGs remains above the threshold value ( $\geq 45$  msec from the baseline; or is  $\geq 500$  msec), then a single ECG must be repeated at least hourly until QTc values from 2 successive ECGs fall below the threshold value that triggered the repeat measurement.

The QTc interval should be recorded using the QTcF (QTc Fridericia) value in milliseconds. In the event that the equipment is not able to provide the QTcF, please use the formula below to calculate.

Formula =  $QT / ((60/HR)^{(1/3)})$

If the average of QTcF values from the triplicate measurements remains above the threshold value ( $\geq 45$  msec from the baseline; or is  $\geq 500$  msec), then a single ECG must be repeated at least hourly until QTc values from 2 successive ECGs fall below the threshold value that triggered the repeat measurement.

If QTcF values remain  $\geq 500$  msec (or  $\geq 45$  msec from the baseline) for greater than 4 hours (or sooner at the discretion of the investigator); or QTcF intervals get progressively longer, the subject should undergo continuous ECG monitoring. A cardiologist should be consulted if QTcF intervals do not return to less than 500 msec (or to  $< 45$  msec above the baseline) after 8 hours of monitoring (or sooner at the discretion of the investigator).

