#### 3.5.3. Vitals and ECGs

Baseline values for vital signs and ECG will be the last completed pre-dose measurement.

If not supplied, QTcF will be derived using Fridericia's heart rate correction formula:  $QTcF = QT / (RR)^{(1/3)}$ , where  $RR = 60/HR$  (if  $RR$  is not provided).

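### The QTcF formula in SAP 6.6.3 carries a stray factor of 1000, so with RR in seconds every value derived from it is one tenth of the Fridericia value in SAP 3.5.3 and Protocol 7.2.5

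*SAP*

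**What the plan says.** Three places in the documents say how QTcF is obtained.

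- **SAP 6.6.3** introduces its formula with "QTcF will be derived using Fridericia's heart rate correction formula" and prints "QTcF(\text{msec}) = QT(\text{msec}) / (RR * 1000)^{1/3". It gives RR in seconds as 60/HR when RR is not provided. It sets no condition on when QTcF itself is derived.
- **SAP 3.5.3** divides QT by the cube root of RR, with RR = 60/HR when not provided. There is no factor of 1000. The derivation is conditional: "If not supplied, QTcF will be derived using".
- **Protocol 7.2.5** divides QT by the cube root of 60/HR. Sites use this formula in one circumstance: "In the event that the equipment is not able to provide the QTcF".

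Section 6.6.3 then specifies the ECG outputs. Triplicates come first: "Any triplicate measurements will be averaged prior to the calculation of summary statistics". QTcF is tabulated in categories cut at 450, 480 and 500 ms ("The number of subjects with average of the triplicate QTcF <450 ms"), and the maximum increase from baseline is cut at 30 and 60 ms. A separate count, "the number of subjects with any single uncorrected QT values" at or above 500 ms, does not use a correction formula.

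ECG belongs to the primary safety endpoints in Protocol 2.2.1, which list "weight, vital signs, ECG, cardiac MRI or echocardiogram measured LVEF" among other items.

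**The concern.** SAP 3.5.3 and Protocol 7.2.5 agree with each other. SAP 6.6.3 names the same method but gives a different formula, and it is the section a programmer would open to build the QTcF tables. If the printed formula is coded, the categories meant to detect QT prolongation cannot do so for derived values.

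The missing condition is a second problem. Section 3.5.3 keeps a supplied QTcF and derives only the gaps. Section 6.6.3, read literally, derives QTcF throughout, since its own condition concerns only where RR comes from. Two programmers working from different sections could produce different datasets: one mostly right, the other wrong in every record. A dataset holding both kinds of value would have QTcF on two scales that differ tenfold.

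**Working it through.** **Inputs.** The three formulas above; RR = 60/HR in seconds, the only RR unit that 6.6.3 states; the cut-points 450/480/500 ms and 30/60 ms from 6.6.3. The QT and heart-rate values below are illustrative, since the documents give none.

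**The factor.** `(RR × 1000)^(1/3) = 1000^(1/3) × RR^(1/3) = 10 × RR^(1/3)`. So the 6.6.3 value divided by the 3.5.3 or Protocol 7.2.5 value is 1/10, whatever QT and heart rate are. Evaluating the formulas at 30 combinations (QT 320 to 500 ms, HR 50 to 120) gave a ratio of 0.1 at every one.

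| QT (ms) | HR | SAP 3.5.3 / Protocol 7.2.5 (ms) | SAP 6.6.3 (ms) |
|---|---|---|---|
| 400 | 60 | 400.0 | 40.0 |
| 420 | 75 | 452.4 | 45.2 |
| 360 | 90 | 412.1 | 41.2 |
| 440 | 90 | 503.7 | 50.4 |
| 340 | 100 | 403.1 | 40.3 |

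**Other unit readings.** If RR is supplied in milliseconds and used as printed, the divisor is `(RR in s × 1,000,000)^(1/3) = 100 × RR^(1/3)`, and the result is one hundredth of the right value. If the multiplication sign were meant as division, RR in seconds would give a result ten times too large. Division by 1000 is right only for RR in milliseconds, which is not the unit 6.6.3 states.

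**Absolute categories.** The QT needed to reach 450 ms under 6.6.3 is `450 × (1000 × 60/HR)^(1/3)`: 4500 ms at HR 60, 4177 ms at HR 75, 3931 ms at HR 90 and 3795 ms at HR 100. No plausible derived value leaves the lowest category.

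**Change from baseline.** Take a true rise from 400 to 460 ms, which is +60 ms and belongs in the top category.

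| Baseline | Post-dose | Change shown (ms) |
|---|---|---|
| supplied | supplied | 460 − 400 = +60 |
| derived | derived | 46 − 40 = +6 |
| supplied | derived | 46 − 400 = −354 |
| derived | supplied | 460 − 40 = +420 |

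With no true change from 400 ms, a derived baseline and a supplied post-dose value show 400 − 40 = +360 ms, a false entry in the category of 60 ms or more.

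**Triplicates.** Suppose all three readings are truly 500 ms. One derived reading gives (500 + 500 + 50)/3 = 350 ms; two give (500 + 50 + 50)/3 = 200 ms; three give 50 ms. In each case the subject moves from the highest category to the lowest. The mix within a triplicate is an assumption.

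**The case against.** The algebra is hard to dispute, so the case on the other side is about reach and weight.

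- **Few values may need deriving.** Protocol 7.2.5 tells sites to record QTcF, and to calculate it with the correct formula where the machine cannot. If that is followed and SAP 3.5.3 governs, derivation in the analysis is only a fallback. This stands as a limit on reach. It does not settle which SAP section governs.
- **The factor of ten depends on RR being in seconds.** RR is itself a listed ECG variable, may often be supplied, and 6.6.3 gives no unit for a supplied value. The condition is fair, but milliseconds make the error larger.
- **The error would be noticed.** Values near 40 ms, or changes of −354 or +420 ms, are conspicuous. Only a triplicate mixing derived and supplied readings gives a plausible-looking average, and nothing in the documents suggests that such mixing is common. This stands, though relying on someone noticing is no reason to leave a wrong formula in the plan.
- **The intent is clear.** Section 6.6.3 names Fridericia, and the correct formula appears twice elsewhere. That makes the correction easy; it does not make the printed text right.
- **Consequences are limited.** The QTcF tables are descriptive. No hypothesis test rests on them, and the site ECG checks in Protocol 7.2.5 and the uncorrected QT count do not use this formula. This also stands.
- **A PDF conversion slip cannot be excluded.** With RR in seconds, however, neither a multiplication nor a division by 1000 is correct, so a misread operator alone would not rescue the formula.

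**Conclusion.** SAP 6.6.3 is wrong as written and contradicts both SAP 3.5.3 and Protocol 7.2.5. The error is an exact factor of ten for each value derived with RR in seconds, and a factor of one hundred if RR is supplied in milliseconds and entered unconverted.

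How many values are affected cannot be determined from the documents. The range runs from none, if every QTcF is supplied and kept under 3.5.3, to all of them, if 6.6.3 is followed literally. The mixed baseline, post-dose and triplicate examples show what could happen and are not estimates of frequency.

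It should be fixed before programming. The formula drives the QTcF tables for a component of the primary safety endpoint, and the error acts against detecting prolongation when the values compared are all derived.

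**What to change.** In SAP 6.6.3:

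1. Delete the multiplication by 1000, so that QTcF is QT in ms divided by the cube root of RR in seconds, as in SAP 3.5.3 and Protocol 7.2.5.
2. State that an RR supplied in milliseconds is divided by 1000 before use.
3. State that QTcF is derived only when it is not supplied. Replacing the formula with a cross-reference to 3.5.3 would cover points 1 and 3 equally well.

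The cost is one formula, one added clause and one line of program code. No data collection, category or other analysis changes.

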#### **6.6.4. Cardiac MRI/Echocardiogram**

*The mean absolute and percent change from baseline in LVEF will be evaluated as compared to placebo and by imaging modality. LVEF shift tables will for sequence and total will be prepared. Exploratory analyses comparing left ventricular wall thickness, ventricular wall strain and cardiac fibrosis against placebo will be performed where data from cardiac MRI are available.*

#### **6.6.5. Liver MRI**

*The mean absolute and percent change from baseline in the R2\* value will be tabulated for each subject. Separate summaries by magnet field strength will be presented. Summaries of the categorical assessment of iron overload (normal, above normal, etc) will be presented. Other exploratory analyses may be performed to compare the treatments.*

#### **6.6.6. Other Safety Data**

Tanner stage, testicular volume, C-SSRS, ratio of bone age to chronologic age (hand and wrist x-ray), bone mineral density (whole body and spine DXA), prior medication(s), non-drug treatment(s), medical history and physical examination will be listed in accordance with the sponsor reporting standards but not subjected to formal statistical analysis.

Any other safety data that is captured on the study database, will be listed.

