### **7.2.3. Tanner Stage and Testicular Volume**

Tanner Staging will be performed according to the [Schedule of Activities](#) to monitor for signs of accelerated sexual development. The physical changes in pubertal development (genital and pubic hair growth) will be assessed using the system described by Marshall and Tanner (Marshall & Tanner 1970). In addition to the Tanner staging, a measurement of testicular size (volume) using orchidometer beads will be documented.

For subjects who may reach sexual maturity during the trial, as indicated by a Tanner Stage V rating, the Tanner Stage, testicular volume, hormone and X-ray (hand and wrist) will no longer be required to be collected to assess for signs of precocious puberty.

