#### 7.9. Triggered Requirements

Condition/ Criteria	Action
Moderate Iron overload/ If the liver iron content estimate as determined by R2* value is above the “mild overload” threshold (R2* >190 Hz at 1.5 T or R2* >369 Hz at 3.0 T)	The subject should be referred to a haematologist for further assessment
Cardiomyopathy/ If the LVEF falls below 50% on the cardiac MRI or echocardiogram at any follow-up visit	The subject should be referred to a cardiologist for further assessment.
Spine compression or fracture/ If either the bone mineral density increases >4% from the start of Period, or if there is a suspicion of a vertebral fracture upon central review of the DXA exam	The subject should have a local spine x-ray performed to confirm the presence or absences of compression or fracture

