### **9.3.5. Other Safety**

Adverse event data, laboratory data and concomitant medications will be tabulated and listed but not subjected to formal statistical analysis.

Other safety data will be listed.

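### Tanner stage, spine bone density and bone age are Period 1 primary safety endpoints, but the SAP only lists them and plans no summary by arm or contrast with placebo.

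*SAP*

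**What the plan says.** Protocol 2.2.1 defines the primary safety endpoints on Period 1 data. One item covers abnormal and clinically relevant change by Week 49. It includes "physical examinations (including nose and throat mucosal exam and Tanner stage" and also "DXA-spine (bone mineral density), x-ray (hand and wrist for bone age evaluation) and C-SSRS". The Protocol Summary says that safety will rest on the incidence of such findings and names DXA bone density and X-ray bone age.

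Testicular volume is not named in 2.2.1. Protocol 7.2.3 adds it to Tanner staging: "In addition to the Tanner staging, a measurement of testicular size (volume) using orchidometer beads will be documented". The stated purpose of the staging is "to monitor for signs of accelerated sexual development".

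SAP 6.6.6 covers Tanner stage, testicular volume, the ratio of bone age to chronologic age, and whole-body and spine BMD. Its whole plan for them is that they "will be listed in accordance with the sponsor reporting standards but not subjected to formal statistical analysis". Protocol 9.3.5 points the same way: "Other safety data will be listed".

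**The concern.** A listing shows each boy's values. It gives no incidence by arm, no mean change and no difference from placebo. The SAP also does not define what counts as abnormal or clinically relevant change for these measures, so the endpoint as worded in Protocol 2.2.1 has no planned output.

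This matters more here than for most safety variables. Boys aged 6 to under 16, all on glucocorticosteroids and with bisphosphonates permitted (Protocol 4.1 and 5.10.1), can be expected to change on all of these measures over 48 weeks without study drug. Accelerated development is a relative idea and needs a comparator. The other planned look, long-term safety in Sequence 1 (Protocol 2.2.4.3), compares each boy with his own baseline, so treatment and growth run together in it. Sequence 3 is the only group never exposed to the drug, and only until its first active dose at Week 49.

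At stake is the maturation and bone part of the primary safety objective. With listings alone, ordinary growth could be read as a drug effect, or a real shift between the arms could go unreported.

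**Working it through.** **1. What each kind of safety data receives.**
- Adverse events: risk differences against placebo, with CIs for tiers 1 and 2 and p-values for tier 1 (SAP 6.6.1).
- Laboratory data (including hormones), vital signs and ECG: summarised by treatment (SAP 6.6).
- LVEF: change compared with placebo (SAP 6.6.4).
- Liver R2*: tabulated, with categorical summaries; comparison of treatments is optional (SAP 6.6.5).
- Lean mass from the whole-body DXA scans: an exploratory endpoint compared with placebo (SAP 3.3.3).
- Tanner stage, bone age, BMD and testicular volume: listed (SAP 6.6.6).

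**2. Whether the data for a contrast exist.** From the Schedule of Activities and Protocol 6.8, in both arms:
- hand and wrist X-ray at screening and Weeks 17, 33 and 49;
- Tanner stage and testicular volume at baseline and Weeks 17, 33 and 49;
- whole-body DXA at screening and Weeks 17, 33 and 49;
- spine DXA at screening and Week 49.

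**3. The plan's own sample size, to fix the arm sizes.** Inputs from Protocol 9.1: difference 2.5 s, SD 4.0 s, two-sided alpha 0.05, power 80%, allocation 2:1, one interim analysis.
- Fixed design: placebo n = 1.5 × [4.0 × (1.960 + 0.842) / 2.5]² = 30.1, so 90.4 in total before rounding, or 31 + 62 = 93.
- One look at 50% information with gamma-family spending: inflation 1.063 for gamma −2 on both boundaries with non-binding futility, giving 90.4 × 1.063 = 96.1. The stated 96 reproduces. The value −2 is an assumption within the stated limit of −1 or less.
- Attrition: 96 / 0.9 = 106.7, against about 105 stated.

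The Period 1 arms are therefore 70 versus 35 enrolled, and 96 completers split 2:1 into 64 versus 32.

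**4. Precision of an active-minus-placebo mean change.** The documents give no SDs for these measures, so results are in SD units, without covariates.
- 70 versus 35: √(1/70 + 1/35) = 0.207; 95% half-width = 1.983 × 0.207 = 0.41 SD.
- 64 versus 32: √(1/64 + 1/32) = 0.217; half-width = 1.986 × 0.217 = 0.43 SD.
- Difference detectable with 80% power: (1.960 + 0.842) × 0.207 = 0.58 SD and (1.960 + 0.842) × 0.217 = 0.61 SD; with the t distribution, 0.59 and 0.61 SD.
- Power for a true difference of 0.5 SD: 67% and 63%.

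**5. Precision for a proportion**, such as the share advancing at least one Tanner stage. The documents give no placebo rate, so 10%, 20% and 30% are assumed. For 70 versus 35, the active rate p₂ detectable with 80% power from placebo rate p₁ solves p₂ − p₁ = 1.960 √[p̄(1 − p̄)(1/70 + 1/35)] + 0.842 √[p₁(1 − p₁)/35 + p₂(1 − p₂)/70], where p̄ is the pooled rate.
- From 10%: 34%.
- From 20%: 47%. Check: p̄ = 0.382, and 1.960 × 0.1006 + 0.842 × 0.0902 = 0.273.
- From 30%: 58%.

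**The case against.** The strongest reply is that listing was a consistent choice and that other routes cover much of the ground.

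- **Consistency.** SAP 6.6.6 follows Protocol 9.3.5. This stands: the SAP does not depart from the protocol's analysis section. The tension is between the endpoint definition in Protocol 2.2.1 and the handling in both documents.
- **The general sentence opening SAP 6.6**, that safety data are summarised to sponsor standards. Those standards are not in the documents, but 6.6.6 names these variables and says what happens to them. The specific rule governs.
- **Adverse events.** Clinically significant examination findings are characterised for adverse event reporting (Protocol 7.2.2). A test result becomes an event if it meets Protocol 8.5, and events then receive a placebo contrast. Individual abnormalities are partly covered. A modest shift of a whole arm in maturation need not make any one boy's result an event. The tier 1 event list is held in the Safety Review Plan, so it is unknown whether bone or puberty events are on it.
- **Low precision.** This stands. A shift of 0.5 SD could still be missed, so the request is for estimates with intervals and not for tests.

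A reader might infer that drug effect cannot be told from growth at all. The documents do not support that. The data are collected by randomised arm, bone age is scaled to chronologic age and read blind to treatment and age (Protocol 7.7.3.2), hormones are summarised by treatment, and the E-DMC reviews unblinded aggregate safety data (Protocol 3.5.2). What is missing is a planned output.

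A reader might also take testicular volume for a primary endpoint, which it is not, or assume that all 105 boys would contribute. Attrition of 10% is assumed, and Tanner staging, testicular volume, hormones and X-ray may stop at Tanner V. Nor is the condition in Protocol 7.9, "bone mineral density increases >4% from the start of Period", an endpoint. It prompts a local spine X-ray, and the plan gives no basis for treating it as an outcome.

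**Conclusion.** The concern holds in this form: three named primary safety endpoints (Tanner stage, spine BMD and bone age) have no planned summary by arm and no planned placebo contrast, although Period 1 supplies a randomised, never-exposed comparator and the measurements are already scheduled. Followed as written, the plan contains no analysis that would separate a drug effect on these measures from growth and puberty.

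The gain from repairing it is real but limited: intervals of about ±0.41 to ±0.43 SD, so that only effects of around 0.6 SD are likely to be shown. These figures assume the planned arm sizes, 2:1 completers and no covariate adjustment. Adjustment would narrow the intervals where baseline value and age predict the change; boys stopping at Tanner V would widen them for bone age and testicular volume. The risk text in Protocol 1.11 is largely blacked out, so how strongly a bone or puberty effect was expected cannot be judged. This is an improvement the sponsor should make. It does not affect the efficacy analysis.

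**What to change.** In SAP 6.6.6, add descriptive Period 1 summaries by arm, Sequences 1 and 2 combined versus Sequence 3:

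- change in the bone-age to chronologic-age ratio at Weeks 17, 33 and 49, with testicular volume at the same visits as a supportive measure;
- percent change in spine BMD at Week 49, with whole-body BMD as supportive;
- a Tanner stage shift table from baseline;
- active-minus-placebo differences with 95% CIs, adjusted for baseline value and baseline age, labelled exploratory and without multiplicity adjustment, in line with SAP 6.6.1.

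For boys whose assessments stop at Tanner V, carry Tanner V forward in the shift table and report the number by arm. Carrying forward does not repair their bone-age and testicular-volume data, which go missing in a way that depends on the outcome. The count by arm lets the reader judge how far that could distort the differences.

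The listings can stay. The cost is a few extra tables, with no new procedures, visits or patients. The drawback is low precision for small effects, which the table footnotes should state so that a wide interval around zero is not read as evidence of no effect.
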